508 For moderator analysis, we will test for interactions by adding interaction terms to the group by 509 time variable for health literacy (limited versus adequate) controlling for prior ACP 510 documentation and clustering effects by clinician. All other interaction terms are adjusted for 511 health literacy (randomization blocking variable) prior ACP documentation and clustering effects 512 by clinician. Additional interaction terms to be added to the group by time variable include 513 decision control preferences for making decisions (i.e., makes own decisions versus doctor 514 makes decisions), age (i.e., < 65 years versus ≥65 years of age), sex/gender (i.e., self-reported 515 man versus woman), race/ethnicity (i.e., white versus non-white), health status (i.e., good-to-516 excellent versus fair-to-poor), presence of a potential surrogate (i.e., yes versus no), and 517 internet access at home (i.e., yes versus no). For Spanish-speakers, we will also asses patient-518 clinician language (concordance vs. discordance). A p-value for interaction <0.05 is considered 519 significant.

520

521 Missing data for the primary outcome will be assessed. If there is 10% or more of missing data, 522 we will use a mean imputation approach and all available data will be included in mixed-effects

models. We will assess whether any research staff member became unblinded during follow-up
 assessment and conduct sensitivity analysis as needed.

525

526 SAMPLE SIZE AND POWER CALCULATIONS

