1143 **PREPARE** has been shown to increase ACP Documentation and Engagement among

Veterans. A prior trial of PREPARE was conducted among 414 Veterans.³⁵ The mean age of 1144 the cohort was 71.1 (7.8) years, 91% were men, 57% were white, 20% had limited literacy, 29% 1145 reported fair-to-poor health status, and 51% had evidence of prior ACP documentation. The 1146 follow-up time point was 6 months and there was a 90% retention rate. There were no 1147 1148 differences in demographic characteristics between study arms. In this VA population, advance 1149 care planning documentation 6 months after enrollment was higher in the PREPARE arm vs the 1150 AD-alone arm (adjusted 35%vs 25%; odds ratio, 1.61 [95%CI, 1.03-2.51]; P = .04). PREPARE 1151 also resulted in higher self-reported ACP engagement at each follow-up, including higher 1152 process and action scores; P <.001 at each follow-up). These findings add further evidence of 1153 the validity of PREPARE. However, PREPARE has never been tested among diverse, English-1154 and Spanish-speaking older adults in a safety-net setting.

1155

1156 OVERVIEW OF THE TRIAL DESIGN

1157 Study overview:

1158 This study is a randomized, controlled trial that uses blinded outcome ascertainment to

1159 determine the efficacy of the ACP PREPARE website to engage ethnically diverse English- and

1160 Spanish-speaking older primary care patients in the ACP process.³⁶ First, we obtained a Health

- 1161 Insurance Portability and Accountability Act waiver to identify individuals who meet our
- 1162 inclusion/exclusion criteria and have upcoming primary care appointments. Administrative data
- and chart review are used to determine potentially eligible patients (Figure, Study Flow Chart).
- 1164

Then primary care clinicians' permission is obtained to allow the study team to inform their patients about the study. Patients are then recruited, screened for eligibility and scheduled for a baseline interview before an upcoming primary care appointment. To standardize the timing of exposure to the intervention and primary care follow-up, study participants are scheduled for baseline procedures 1-3 weeks prior to an upcoming primary care appointment.²⁸

1170

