Next, informed consent is obtained, and those patients who provide consent are randomized to the PREPARE intervention arm (i.e., the PREPARE website with action plan exercises plus an easy-to-read advance directive plus PREPARE materials to take home, which include a website login, and a PREPARE pamphlet, booklet, and DVD) or the control arm (i.e., an easy-to-read advance directive alone). See Study Flow Figure and a full description of the intervention below.

1177 We then conduct blinded outcome ascertainment by performing chart reviews to determine ACP 1178 documentation at baseline and at the end of the study. We also conduct blinded outcome ascertainment using patient surveys at 1 week, and 3, 6, and 12 months after the primary care 1179 1180 appointment. We are choosing an active control arm (i.e., an easy-to-read advance directive) 1181 because we believe provision of an advance directive for chronically and seriously ill older 1182 patients should be the standard of care, even if it is not often "usual" care in clinical practice.⁸ In 1183 addition, the easy-to-read advance directive used in this study has been adopted by the San 1184 Francisco Health Network (SFHN) and Zuckerberg San Francisco General Hospital (ZSFG) and 1185 is available in the primary care clinics.

1186

1187 **Research Aims and Study Hypotheses:**

1188 The aims of this study are to (1) To determine the efficacy of PREPARE to engage diverse,

1189 English- and Spanish-speaking older adults with chronic illness in advance care planning (ACP)

1190 compared to controls (AD only) and (2) To determine whether PREPARE efficacy varies by

race/ethnicity, literacy, clinician-patient language concordance, and patient's desired role in
 decision making.³⁶

1193

Our primary hypothesis is that the PREPARE program plus an easy-to-read advance directive
will result in greater documentation of ACP wishes, including advance directives and
documentation of ACP discussions in the medical record, than an easy-to-read advance
directive alone in elderly populations with chronic illness.

1198

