 when they were randomized, they receive a brief reminder call one to 3 days before their
 primary care appointment date. We conduct follow up assessments at 1 week, and at 3, 6,
 and 12 months from this primary care appointment date,
- If they do not reschedule or attend their primary care appointment within 6 months from
 when they were randomized, they receive a brief reminder call one to 3 days before their
 new primary care appointment date. We conduct follow up assessments at 6 and 12 months
 from the originally scheduled primary care appointment date.
- 1529

Ascertaining reasons for loss of follow-up or withdrawal: For participants who want to withdraw, we ask them why in open-ended questions. If they cannot provide an answer, we prompt them from a list of reasons we obtained from prior advance care planning trials, such as the study is too long, they are too busy, the study topic is too upsetting, they are too ill, etc.³⁵

- 1535 **MEASURES**
- 1536 **Overview**

1537 Because ACP ideally is a process that occurs over time, we felt it important to measure a full 1538 range of ACP measures including ACP documentation (primary outcome) over time, and 1539 several behavior change constructs and several additional ACP actions over a 12-month period 1540 (secondary outcomes). All study measures used in this analysis, including validity and reliability 1541 information in English and Spanish and the schedule of administration (i.e., baseline, 1-week or 1542 3, 6, or 12-months), are included in the Outcome Measures table below. All outcomes, including 1543 secondary outcomes not used in our main analysis, are included in our published protocol.³⁶ 1544 The main outcome measures are described in detail below.

1545

1546 **Primary Outcome**

The primary outcome is new documentation of ACP wishes in the ZSFG/SFHN medical record (Table of Outcome Measures below). ACP documentation for the purposes of this study includes the easy-to-read advance directive or other valid advance directives or living wills, a durable power of attorney for health care document (DPOAHC), a Physicians Orders of Life Sustaining Treatment form, or other documentation of discussions concerning patients' wishes for medical care (i.e., documentation of oral directives by a physician or notes describing patients' goals for medical care by clinicians).

1554

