1555 We assess baseline and 15-month new ACP documentation rates and the date of 1556 documentation to determine the length of time from study enrollment to subsequent 1557 documentation. Patients in our study are enrolled, randomized, and exposed to the intervention 1558 1 to 3 weeks prior to a primary care appointment. ACP documentation is timed to the date of 1559 intervention exposure as patients may have engaged in ACP prior to seeing their primary care 1560 provider. The patient-reported outcomes in the follow-up surveys (1 week, 3, 6, and 12-months), 1561 however, are timed to the primary care visit because those questions concern engagement in 1562 discussions with clinicians (see secondary outcomes below). This same timeframe for ACP

- documentation was determined from a prior PREPARE trial conducted within the VA to take into
- account and to standardize the expected time from intervention exposure to the primary care
- 1565 visit and the anticipated time to schedule and complete the final patient interview.³⁵
- 1566

Because legal forms and documented discussions can be used to direct medical care, we created a composite variable of any ACP documentation (forms and/or discussions); we also plan to report the percentage of forms and discussions separately. All medical review data is double coded by 2 independent, blinded research assistants. Discrepancies are adjudicated by the principal investigator ([name]).

1572

1573 Secondary Outcomes

1574 Main Patient-Reported Outcome

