1649 Our primary analyses will compare change in ACP documentation between study arms from 1650 baseline to 15 months. Secondary outcomes will include ACP Engagement with respect to 5 1651 ACP Actions (yes/no and a 0-25-point scale) and behavior change scores (average 5-point 1652 Likert scores) from baseline to 1 week, and 3, 6, and 12 months. Variables will be assessed for distributional and outlier values using standard summary statistics. Baseline comparability will 1653 1654 be assessed between groups using unpaired t-tests, Chi-square tests or Fisher's exact tests. 1655 Using t-tests or Chi-squared tests, we will also compare patient's age and self-reported gender 1656 between those who refused versus those who enrolled and differences between arms of those 1657 who withdrew versus those who did not. We will use intention-to-treat analysis using SAS 1658 version 9.4 (SAS Institute Inc.) and STATA 15.0 (College Station, TX). All p-values will be 2-1659 tailed and set at .05 for the primary outcome and Bonferroni adjusted for secondary patient-1660 reported outcomes. In addition, because of differences in ACP engagement among English and Spanish speakers,⁸ and based on preferences of our stakeholders and granting agencies, we 1661 1662 decided, a priori, to analyze our results overall and stratified by English and Spanish language. 1663 To compare outcomes between the two arms longitudinally, we will use mixed effects linear, 1664 Poisson, or negative binomial regression for continuous measures and mixed effects logistic regression for dichotomous measures. The mixed effects models will include fixed effects for the 1665 1666 primary modeling terms of time (baseline and 15 months for ACP documentation and baseline 1667 and 1 week, 3 months, 6 months, and 12 months for ACP Engagement with time modeled using 1668 dummy variables to allow for non-linearity); arm (AD-only versus PREPARE); an interaction 1669 term of study arm and time; and a random effect for subjects. We will adjust for the randomization blocking factors limited vs. adequate literacy,⁹⁸ and any predictor variables that 1670 1671 differ between arms. All models also will also be adjusted for baseline ACP documentation and will include random physician intercepts to account for nesting of patients within physicians. We 1672 1673 will use standardized, clinically meaningful effect sizes (i.e., 0.20-0.49 small, 0.50-0.79 medium,

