and ≥ 0.80 large).⁹⁹ Per stakeholder request, we will conduct post-hoc mixed-effects regression to calculate the percentage of participants who increased their Behavior Change score, Action scores, or both Behavior Change and Action scores from baseline (i.e., estimated slope > 0) by study arm; p-values adjusted to a significance of 0.017.

1678

1679 For moderator analysis, we will test for interactions by adding interaction terms to the group by 1680 time variable for health literacy (limited versus adequate) controlling for prior ACP 1681 documentation and clustering effects by clinician. All other interaction terms are adjusted for 1682 health literacy (randomization blocking variable) prior ACP documentation and clustering effects 1683 by clinician. Additional interaction terms to be added to the group by time variable include 1684 language (i.e., English versus Spanish), control preferences for decision making (i.e., makes 1685 own decisions versus doctor makes decisions), age (i.e., < 65 years versus \geq 65 years of age), 1686 sex/gender (i.e., self-reported man versus woman), race/ethnicity (i.e., white versus non-white), 1687 health status (i.e., good-to-excellent versus fair-to-poor), presence of a potential surrogate (i.e., 1688 yes versus no), internet access at home (i.e., yes versus no), and, for Spanish-speakers, 1689 patient-clinician language (concordance vs. discordance). A p-value for interaction <0.05 is 1690 considered significant. 1691

Missing data for the primary outcome will be assessed. If there is 10% or more of missing data, we will use a mean imputation approach. All available data will be included in mixed-effects models. We will assess whether any research staff member became unblinded during follow-up assessment and conduct sensitivity analysis as needed.

1696

1697 SAMPLE SIZE AND POWER CALCULATIONS

1698 We will measure a full range of ACP behaviors including discussions. However, written advance 1699 directive completion of legal forms is a primary outcome and is the most well-studied.¹⁰⁰ Power

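### Mean imputation is prescribed for a yes/no primary outcome; it does not fit the planned logistic model, and how imputed values would enter it is not stated

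*Combined protocol and SAP*

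**What the plan says.** All references are to the final protocol (September 2017) unless noted.

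- **Outcome.** Measures, Primary Outcome: "The primary outcome is new documentation of ACP wishes in the ZSFG/SFHN medical record". Legal forms and documented discussions are combined into one composite of any documentation, so each participant is a yes or a no. The outcome is found by blinded chart review.
- **Model.** The Statistical Analysis Plan assigns "mixed effects logistic regression for dichotomous measures", with baseline and 15 months as the time points for documentation. Two-sided alpha is 0.05.
- **Missing data.** The same section says missing data for the primary outcome will be assessed, and then: "If there is 10% or more of missing data, we will use a mean imputation approach". The next sentence reads: "All available data will be included in mixed-effects models". The only sensitivity analysis named in that paragraph concerns unblinding of staff.
- **Original protocol.** The two statements stood there in one sentence: "we will use a mean imputation approach and all available data will be included in mixed-effects" models. The authors evidently saw them as compatible, so this is not a contradiction.

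**The concern.** A logistic model takes responses of 0 or 1. At the rates the documents use, an imputed mean lies strictly between them. To apply the rule, the analyst must therefore add a step the plan does not contain: choose an arm, stratum or pooled mean, round it, or move to another model. The plan also does not say whether the available-data sentence includes the imputed values or which result is primary once 10% is reached.

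Mean imputation as written fills each gap with a single value and treats it as observed, so no imputation uncertainty reaches the standard error. The primary result would depend on a choice that could be made after the data are seen. Some choices favour a positive finding and others dilute the effect.

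**Working it through.** **The plan's own power figures.** With 175 per arm, pooled variance under the null and two-sided alpha of 0.05, 15% vs 30% gives 92.3% power (stated 92%) and 15% vs 27% gives 79.0% (stated 80%). Both reproduce closely. They concern complete data and do not bear on the imputation rule.

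**Inputs.** Advance directive rates of 15% vs 27%, from Sample Size and Power Calculations. Documentation rates of 25% vs 35%, from the Veterans trial in Preliminary Studies (adjusted, 6 months). Recruitment target of 804, or 402 per arm across both languages.

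**Assumptions, not taken from the documents.** A share *m* is missing completely at random, equally in each arm. One time point, two proportions, binomial variance. I use *m* = 10% (the trigger) and 15%.

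**Reading 1: arm mean.** The estimate is unchanged, but the variance is computed as if all *n* were observed. The standard error is multiplied by √(1−m), and the type I error is 2·[1−Φ(1.96·√(1−m))].
- m = 10%: factor 0.949; type I error 0.063; coverage of the 95% interval 93.7%.
- m = 15%: factor 0.922; type I error 0.071; coverage 92.9%.

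These do not depend on the rates.

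**Reading 2: pooled mean. Reading 3: mean rounded to 0** (every mean here is below 0.5). In both, the difference becomes (1−m) × the true difference.

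| Rates | m | Difference, points | OR, full data | OR, pooled mean | OR, rounded to 0 |
|---|---|---|---|---|---|
| 15% vs 27% | 10% | 12.0 → 10.8 | 2.10 | 1.94 | 2.06 |
| 15% vs 27% | 15% | 12.0 → 10.2 | 2.10 | 1.87 | 2.04 |
| 25% vs 35% | 10% | 10.0 → 9.0 | 1.62 | 1.54 | 1.58 |
| 25% vs 35% | 15% | 10.0 → 8.5 | 1.62 | 1.50 | 1.57 |

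Worked case, 15% vs 27%, m = 15%, pooled mean 21%: control 0.85 × 15 + 0.15 × 21 = 15.9%; PREPARE 0.85 × 27 + 0.15 × 21 = 26.1%.

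Type I error with the pooled mean is 2·[1−Φ(1.96/√(1−m))] = 0.039 and 0.034, so it is not inflated.

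**Power, 402 per arm, 25% vs 35%, m = 15%.**
- Available data: n = 0.85 × 402 = 341.7 per arm; SE = √[(0.1875 + 0.2275)/341.7] = 0.0349; 0.10/0.0349 − 1.96 = 0.91; power 82%.
- Pooled mean: expected difference 0.085, reported SE 0.0322, true SD 0.85 × 0.0349 = 0.0296; (0.085 − 1.96 × 0.0322)/0.0296 = 0.74; power 77%.
- Rounded to 0: reported SE 0.0306; 0.085/0.0306 − 1.96 = 0.82; power 79%. This treats missingness as varying at random by patient; with exactly equal missing shares fixed in each arm it is 80%.

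**Simulation check.** 200,000 trials per setting, null rates 15% and 25%, 201 and 402 per arm.

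| Handling | Type I error, m = 10% | Type I error, m = 15% |
|---|---|---|
| Available data | 0.050–0.052 | 0.050–0.052 |
| Arm mean | 0.062–0.065 | 0.072–0.074 |
| Pooled mean | 0.038–0.041 | 0.034–0.035 |
| Rounded to 0 | 0.047–0.048 | 0.046–0.049 |

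**Trigger.** 10% of 804 is 80.4, so 81 missing; 10% of 402 is 40.2, so 41 if the rule is applied within one language group. Both counts assume one outcome per recruited participant; the plan does not define the denominator.

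**The case against.** The strongest reply is that the rule will probably lie dormant. The outcome is read from the medical record, so a missed interview does not make it missing, and a reviewed chart with no entry is a no. The 15% dropout in the sample-size section is not the share of missing charts. This stands, and it limits the practical weight of the point. It does not remove it. The 10% trigger was written for this outcome, so the rule must be workable. The plan also does not say whether charts of withdrawn participants are still reviewed, or what counts as a missing chart outcome.

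Second, the available-data sentence is already the core of a sound analysis. That is true, but it leaves the imputation sentence in force.

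Third, some logistic routines accept fractional responses as a quasi-likelihood, so strict impossibility is not shown. This too is fair. But the plan does not choose that route, and treating imputed values as observed would still carry no imputation uncertainty.

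Fourth, the effects are modest, and only the arm mean inflates the type I error. At the 10% trigger, power for 25% vs 35% with 402 per arm is 84% on available data, 81% with the pooled mean and 83% with zero. That is correct. The losses are small but avoidable.

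**Conclusion.** The concern holds. The plan prescribes a method that does not suit a yes/no outcome, and each of the three readings examined does worse than the available-data analysis. Arm means understate the standard error by 5% at 10% missing and 8% at 15%. The pooled mean and rounding to zero shrink the difference by 10% and 15%.

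The numbers are illustrations. They rest on data missing completely at random, equal shares per arm and a single-time-point comparison. They do not come from the planned mixed model with subject and physician effects, literacy and baseline documentation. Confidence is high about the rule as written and low that it will be triggered. It should be fixed before analysis because the correction is cheap and closes a choice in the primary analysis.

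**What to change.** 1. Delete the mean-imputation sentence.
2. State that the mixed logistic model on all available outcomes is the primary analysis, whatever share is missing.
3. Define a missing chart outcome, as distinct from a reviewed chart with no planning entry, and give the denominator for the 10% rule.
4. If 10% or more is missing, add two sensitivity analyses: multiple imputation suited to a binary outcome, and an analysis counting missing as no new documentation. The second is numerically the same as rounding to zero. It is acceptable as a labelled sensitivity analysis but not as the primary estimate. The imputation covariates are for the sponsor's statistician to choose.

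The cost is SAP wording and modest programming in SAS or Stata, both already named. The drawback is that the available-data model assumes outcomes are missing at random given its terms, which is why the sensitivity analyses are needed.

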1700 from longitudinal analyses with repeated measures will be stronger, but to be conservative, we consider power for a single post-intervention time point (e.g., 15 months). A recent meta-1701 1702 analysis of written advance directive documentation studies demonstrated a pooled effect size of 0.50 (95% CI; 0.17 -0.83),¹⁰⁰ as did an RCT of an ACP workbook that included both behavior 1703 change constructs and a social work visit,¹⁰¹ and our prior RCT of an easy-to-read AD at ZSFG 1704 which showed an increased AD completion rate from 7% to 15%.⁸ Because both the 1705 1706 intervention and control arm will receive the easy-to-read advance directive, we assume that 1707 both arms will have an advance directive completion rate of $\leq 15\%$. Based on prior studies, we 1708 assume PREPARE will result in additional benefit of advance directive completion with a 1709 minimum effect size of 0.5 (two-fold increase) above 15%. A sample of 350, (175 per arm), will 1710 afford us 92% power (2-tailed alpha of 0.05) to detect a difference of advance directive 1711 completion rates of 15% in controls vs. 30% in the PREPARE arm and 80% power to detect a difference of 15% vs. 27%. Power is also expected to be strong for the ACP behavioral change 1712 scale outcomes (preliminary data demonstrated a pre-to-post improvement of 0.5 SD).²⁷ With a 1713 1714 conservative assumption that controls will improve by 0.1 to 0.2 SD, we will have 85% to 98% 1715 power, respectively, to conclude that the improvement is better in the PREPARE arm. We 1716 expect a 15% drop out rate at 12 months based on our prior randomized, controlled trial at ZSFG,⁸ and will therefore attempt to recruit 402 patients, or 201 in each arm for each language 1717 1718 (English and Spanish) for a total recruitment of 804 patients.

1719

Our sample size will also allow adequate power to detect clinically important interactions based on potential moderators (literacy, control preferences, language concordance) for our outcomes. In a prior trial of an easy-to-read advance directive in the same patient population with only 200 patients, we found significant interactions for literacy.⁸ Thus, if we consider the power scenario of the control group ACP documentation rate of 15% and the PREPARE group of 28%, and suppose the control group rate is the same (15%) for both levels of the moderating factor, then

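### The claim that the stated 92% and 80% power are conservative is unsupported for the primary outcome: documentation has one post-intervention reading, and the figures belong to a 15-month comparison, not the planned change contrast

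*Combined protocol and SAP*

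**What the plan says.** All references are to the final protocol (September 2017).

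- **Sample Size and Power Calculations.** Power "from longitudinal analyses with repeated measures will be stronger, but to be conservative, we" "consider power for a single post-intervention time point (e.g., 15 months"). The numbers follow: "A sample of 350, (175 per arm), will" "afford us 92% power (2-tailed alpha of 0.05) to detect a difference of advance directive" "completion rates of 15% in controls vs. 30% in the PREPARE arm and 80% power to detect a" difference of 15% vs 27%. The sample is then inflated for dropout and doubled, because each language is sized separately (402 per language, 804 in all).
- **Statistical Analysis Plan.** "Our primary analyses will compare change in ACP documentation between study arms from" baseline to 15 months. The model for a binary outcome is mixed-effects logistic regression with arm, time, arm by time, a random subject effect and a physician intercept. Time has two levels for documentation. All models are also adjusted for baseline documentation and for literacy. Results are reported overall and by language.
- **Overview of the Trial Design and Outcome Measures Table.** Chart review determines "documentation at baseline and at the end of the study"; the table marks only baseline and 15 months. The 1-week and 3-, 6- and 12-month readings belong to the patient-reported outcomes.
- **Primary Outcome.** The outcome is defined as new documentation.

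**The concern.** A reader takes from the power section that 92% and 80% are floors, and that the planned analysis will do better because it uses repeated measures. For documentation there is no series of post-intervention readings to supply that gain. The only additional reading is the baseline, and it is used in one of two quite different ways. As a covariate in a 15-month comparison it costs little and may help. Subtracted in a change contrast, it adds its own sampling noise, which on the log-odds scale is large when the baseline rate is low. The SAP contains both elements and does not say which one is the primary test.

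At stake is how a null result is read, especially in one language. If the change contrast is the test and its power is well below the printed figure, a non-significant result could be taken as evidence against the two-fold effect the trial was sized for.

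**Working it through.** **1. Reproduce the stated figures.** Inputs from the power section: 175 per arm, two-sided 0.05, 15% vs 30% and 15% vs 27%. Power = Φ[(d − 1.96·SE0)/SE1], with SE0 from the pooled rate and SE1 from the separate rates.

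- 15% vs 30%: SE0 = √(2 × 0.225 × 0.775/175) = 0.0446; SE1 = √((0.1275 + 0.21)/175) = 0.0439; Φ[(0.15 − 0.0875)/0.0439] = 92.3% (unpooled 92.7%).
- 15% vs 27%: SE0 = 0.0435; SE1 = 0.0431; Φ[(0.12 − 0.0853)/0.0431] = 79.0% (unpooled 79.6%).

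The stated figures are therefore those of two proportions compared once, within one language.

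**2. Power of the change contrast.** Let b be the baseline rate (equal in both arms), p the 15-month rate and c the within-person covariance. On the marginal log-odds scale:

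- effect = logit(p in PREPARE) − logit(p in control)
- variance per arm = [1/(b(1−b)) + 1/(p(1−p)) − 2c/(b(1−b)p(1−p))]/n
- power = Φ(effect/SE − 1.96)

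If documents are counted in separate before and after windows, c = ρ√(b(1−b)p(1−p)). If every baseline document carries forward (cumulative counting), c = b(1−p).

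The plan gives neither b nor ρ for this trial, nor the counting rule, so all three are assumptions here. The 7% is the lower rate from the earlier trial at this hospital.

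Worked case: b = 7%, ρ = 0, 15% vs 30%. Effect = ln(0.30/0.70) − ln(0.15/0.85) = 0.887. SE² = (15.361 + 7.843 + 15.361 + 4.762)/175 = 0.2476, so SE = 0.498. Power = Φ(1.783 − 1.96) = 43%. Without the two baseline terms, SE² = (7.843 + 4.762)/175 = 0.0720, SE = 0.268 and power is 91%. The loss comes from the baseline terms.

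| Baseline and counting | 175/arm, 15 vs 30% | 175/arm, 15 vs 27% | 350/arm, 15 vs 30% |
|---|---|---|---|
| 7%, separate, ρ 0–0.4 | 43–61% | 32–46% | 71–88% |
| 7%, cumulative | 71% | 56% | 94% |
| 10%, cumulative | 91% | 80% | over 99% |
| 12%, cumulative | 98% | 92.5% | over 99% |
| 15%, separate, ρ 0–0.4 | 60–81% | 45–65% | 88–98% |
| 30%, separate, ρ 0.5 | 94% | 83% | over 99% |

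Under cumulative counting, the change contrast matches the post-only log-odds comparison when 2/[b(1−b)] = [2/(1−b)] × (1/0.15 + 1/0.30), that is b = 1/10. Below 10% it loses power; above 10% it gains.

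Small simulations of the random-intercept logistic model (100–300 runs per case, no covariates or physician effects) point the same way. At correlation 0.3 they gave 62–67% for baseline 7% and 73–76% for baseline 15%.

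**3. Baseline-adjusted comparison at 15 months.** Simulated logistic regression of 15-month documentation on arm and baseline documentation, 175 per arm, gave about 92–96% for 15% vs 30% and about 77–82% for 15% vs 27%. A further check (1,000 runs per case; baseline 7%, 15% and 30%; correlation 0 and 0.3) gave 92–94% and 79–84%. The stated power belongs, near enough, to this test.

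**The case against.** The strongest case on the other side has four parts.

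- **The plan can be read as the baseline-adjusted analysis.** The outcome is new documentation, and every model adjusts for baseline documentation. On that reading 92% and 80% are about right. This stands, and it is why the fix names that comparison. It does not rescue the reason given, since repeated post-intervention readings still do not exist for this outcome.
- **The change contrast can match or exceed 92%.** Carry-forward counting at baseline 12%, or baseline 30% with correlation 0.5, does so. A change analysis on the risk-difference scale also often loses less (for example 92% at baseline 7%, correlation 0.3), although the SAP specifies logistic regression. This stands.
- **The 7% anchor is weak.** The power section presents it as a starting rate, while Preliminary Studies also gives 15% vs 7% as a comparison of arms. It covers advance directives only, whereas the primary outcome includes documented discussions. The only rate of prior ACP documentation in the documents is 51%, from the Veterans trial; on the log-odds scale that gives 73–91% for correlation 0–0.4. This stands.
- **175 per arm is one language.** The pooled analysis has about 350 per arm and more power. This stands, but the plan sizes each language separately and commits to stratified results, so per-language power is the quantity it states.

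The longitudinal statement is also plausible for the engagement scores, which do have four follow-up readings. The sentence, however, introduces the documentation rates.

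**Conclusion.** The point holds as a lack of support. The plan calls 92% and 80% conservative for a reason that does not apply to the primary outcome, and the figures describe a different contrast from the change analysis the SAP names. This much follows from the text and from reproducing the figures, without further assumptions.

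A reader might go further and infer that the primary analysis has only 43–81% power, or that the plan's sentence is false. The documents do not support either. That range needs a baseline of 7–15%, a correlation of 0–0.4, separate-window counting, the log-odds scale and a single language. Other admissible inputs reach 92% or more, and pooling both languages gives 71–88% at baseline 7% and 88–98% at baseline 15% under the same counting. The direction and size of the difference cannot be settled from the plan. The simulations behind the model-based figures are modest in size and leave out physician effects.

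**What to change.** **Sample Size and Power Calculations.** Delete the statement that longitudinal power will be stronger and that the calculation is therefore conservative. Put in its place: *The 92% and 80% are the power of a two-sided 0.05 comparison of the arms at 15 months with 175 per arm within a language. Documentation has a single post-intervention reading, so no longitudinal gain is assumed.*

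**Statistical Analysis Plan.** Name the primary test: *the arm odds ratio for new documentation at 15 months, adjusted for baseline documentation and literacy*, with the physician intercept already planned. This uses terms that are in the plan and keeps roughly the stated power.

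If the arm-by-time contrast is kept instead, state how documents are counted before and after exposure, and restate its power, per language and pooled, over a stated range of baseline rate and correlation.

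**Cost.** Wording in two sections; no extra patients or data. The claimed safety margin is lost, and the primary contrast is described as an adjusted 15-month comparison instead of a change. The second is a real choice of what is estimated and should be recorded as such.
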